### **3. Risk of excess inhaled corticosteroid use**

As mentioned in the risk section, we anticipate, based on the efficacy data, that ICS use will actually decrease over the course of the study. Patients will be cautioned about steroid side effects and told to report them to their physician. We will also work with our sites, patients, and providers to review additional precautions.

### **4. Adverse Event Monitoring**

#### **(a) Asthma-Related Adverse Events:**

Data collection will include assessment of exacerbations, with confirmation through communication with the patient's primary site of asthma care. Due to the pragmatic nature of the study, no additional interventions will be provided unless the patient has an allergic reaction to the components of the ICS used for this study.

#### **(b) Non-Asthma Adverse Events**

We won't monitor these due to the nature of pragmatic trials like this one. However, adverse events due to concurrent illnesses other than asthma may be grounds for termination from the trial if the illness is considered significant by the investigator or the patient's personal physician or other clinician or if the patient is no longer able to participate effectively in the study. Patients experiencing minor intercurrent illnesses may continue in the study. Examples of minor intercurrent illnesses include acute rhinitis, sinusitis, upper respiratory infections, urinary tract infections, and gastroenteritis. Because this is a pragmatic trial, no restrictions on medications for treatment of these conditions will be made.

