The analyses on the exploratory outcomes will also be performed. The rate on asthma deteriorations will be reported by treatment groups. The composite endpoint of asthma deteriorations or exacerbations will be analyzed using the same Andersen-Gill version of the Cox proportional hazards model as used in the primary analysis. The Asthma APGAR data will be analyzed using the same mixed model approach as described above in the Asthma Control Test (ACT) score analyses.

Data on the Asthma Medication Ratio (AMR) during the follow-up months, the total health care utilization (i.e., total number of visits made to the enrolling sites, total number of ED visits, and total number of hospitalizations), and asthma related health care utilization (i.e., number of visits made to the enrolling sites, number of ED visits, and number of hospitalizations for which asthma is a first or second diagnosis) will be summarized. Differences between two randomized treatment groups on these variables will be compared using either t-test or Kruskal-Wallis test if full follow-up is available on everyone or Poisson or Negative Binomial regression models with time as an offset to account for differential duration of follow-up.

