## **9. Interim Analysis**

It is anticipated that our independent safety officer will review the accumulating data at approximately 6-month intervals. Interim data analyses of the key safety and outcome data will be performed in a blinded fashion for each of these data reviews. The primary objective of these analyses will be to evaluate the accumulating data. Our independent safety officer will review the clinical outcome rates, patient recruitment, compliance with the study protocol, reasons and patterns of the missing data, adverse event rates and other factors that reflect the overall progress and integrity of the study.

Before each independent safety officer review session, a blinded summary safety data report will be provided to the safety officer. The extracted data files and the analysis programs for each independent safety officer report will be archived and maintained at the Statistical Data CC for the life of the study.

We will monitor the event rate as it accumulates in a blinded fashion to help us determine if we will achieve sufficient power. We will also review the baseline characteristics of enrolled participants to make sure we have enrolled the population defined in the protocol.

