For the primary analysis (Andersen-Gill model) subjects discontinuing the study prematurely will be censored at the time of discontinuation. This approach might lead to biased results if discontinuation does not occur at random. Thus, two sensitivity analysis will be undertaken to examine the sensitivity of inference when data is missing at random and not at random: 1. Inverse probability weighting. In this approach, contribution of each subject to the risk set calculated at time  $t$  will be inversely weighted by the estimated probability of remaining uncensored up to time  $t$ . This probability will be estimated using a Cox proportional hazards model fitted to time to censoring with variables potentially prognostic of both, failure and censoring, both baseline and time- dependent (such as most frequent major protocol deviations, certain AEs etc.), entered as covariates. In order to reduce potentially high variability of the resulting treatment effect estimators due to sampling variability in weights, the weights will be “stabilized” by multiplication of probabilities of remaining uncensored up to time  $t$  estimated using baseline covariates only. 2. Pattern-mixture approach. As per Little 2012. we will assume that for participants who drop out, the hazard of an outcome deviates from that of participants who do not drop out by an offset- $r_1$  for treatment and  $r_0$  for placebo. We will then explore the effect of this deviation on the findings for various choices of the offsets in the two study groups. If the treatment effect is qualitatively maintained for the range of offsets that are considered to be clinically plausible, then the findings will be considered to be robust.

In other analyses, missing data will be handled by using multiple imputation. Ten imputed data sets will be generated with imputation methods based on the regression or Monte Carlo framework. Final results will be based on averages from the ten imputed data sets with appropriate estimator employed of the variance. The variables included in the imputation model as covariates will be pre-specified.

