### **2. Inhaled Corticosteroids Risks**

All subjects will already have been on daily ICS maintenance therapy prior to enrollment in the study. ICS therapy is currently commonly used for asthma but not approved for use as rescue therapy—ICS as rescue therapy is what the intervention group will be asked to do (PARTICS). Participants assigned to the intervention group will be provided with the ICS beclomethasone dipropionate (QVAR® RediHaler™ (beclomethasone dipropionate HFA)) and asked to use one puff of it for every puff of albuterol used for rescue. Overall corticosteroid dosing may be increased in the intervention group, especially in the short term. However, data from efficacy studies of the PARTICS approach suggest that total inhaled corticosteroid dose will actually decrease as providers decrease the ICS dose due to improved patient control. Additionally, since we are targeting a group that has a high risk of exacerbation (1/3 or more based on our prior studies) for many subjects the total yearly dose of corticosteroids will be decreased even further due to avoidance of oral corticosteroid bursts resulting from the decreased rate of asthma exacerbations with PARTICS.

All subjects will be informed that beclomethasone dipropionate/QVAR® RediHaler™ (beclomethasone dipropionate HFA) can most commonly produce:

- hoarseness,
- throat irritation, and
- yeast infection of the mouth or throat (known as thrush or oral candidiasis,

We will advise participants to rinse their mouths with water and spit the water with each inhaler

use in order to avoid these side effects. We will inform participants that other less common risks with use of beclomethasone dipropionate/QVAR® RediHaler™ (beclomethasone dipropionate HFA) may occur, although many of these side effects usually occur when corticosteroids are taken orally, not inhaled, and have been reported in children. These include:

- Osteoporosis
- Glaucoma
- Cataracts
- Adrenal gland suppression

Pregnancy is not a contraindication to asthma controller therapy, including ICS. Improved asthma control has been shown to be associated with improved pregnancy outcomes. We will advise all women to seek maternity care as soon as they are aware of the possibility of pregnancy and to inform their physician or nurse midwife of their participation in this study.

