## **6. Data and Safety Monitoring Plan**

We will appoint an independent safety officer from the Division of Pulmonary and Critical Care Medicine from Brigham and Women's Hospital who has no other role in the PREPARE trial. This independent safety officer will be presented data in a blinded manner, and review safety data twice annually.

The PI of the study will be informed of serious adverse events as soon as they occur and will notify the central IRB at Partners within 5 working days/7 calendar days.

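### The protocol declines to monitor non-asthma adverse events yet promises all-cause SAE reporting, with no described way for a non-asthma SAE to reach the PI

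*Combined protocol and SAP*

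**What the plan says.** Section VII.C.4 splits adverse events into asthma-related, non-asthma and serious. For the asthma-related group it collects exacerbations. For the non-asthma group it says "We won't monitor these due to the nature of pragmatic trials like this one", although the same paragraph adds that "adverse events due to concurrent illnesses other than asthma may be grounds for termination from the trial".

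Section VII.B.2 lists the ICS side effects that participants are told about. Three are described as common (hoarseness, throat irritation, thrush) and four as less common (osteoporosis, glaucoma, cataracts, adrenal suppression). VII.C.3 gives the route for reporting them: "Patients will be cautioned about steroid side effects and told to report them to their physician". The end of VII.B.2 likewise sends patients to their doctor or nurse.

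The SAE definition in VII.C.4(c) is not limited to asthma. VII.C.6 promises: "The PI of the study will be informed of serious adverse events as soon as they occur", followed by notice to the central IRB within five working days or seven calendar days. III.E.9 has the independent safety officer look, about every six months, at "reasons and patterns of the missing data, adverse event rates and other factors".

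**The concern.** The listed side effects of the study drug fall in the class that the protocol says it will not follow. An admission or death from a cause other than asthma falls in that class and also meets the SAE definition. A site that follows VII.C.4(b) to the letter has no instruction that would let the PI meet VII.C.6 for such an event.

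This matters because the intervention adds ICS to a maintenance regimen that already contains it. VII.B.2 accepts that corticosteroid dosing may rise in the intervention arm, particularly early on, although it expects the total to fall later as providers step doses down. Section I.B.7 records that patient partners were worried about excess ICS use. If the trial shows fewer exacerbations, readers will want to set that against side effects, and the plan describes no systematic collection of them.

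**Working it through.** No arithmetic applies beyond a count. The check is to follow each listed risk and each promised report to a source of data.

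1. **Listed ICS side effects (VII.B.2).** 3 common + 4 less common = 7. All seven are non-asthma, so VII.C.4(b) applies to all seven. The only stated destination for a report is the patient's own clinician (VII.B.2, VII.C.3), and no return path to the study is described. Result: 7 of 7 have no described collection procedure.

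2. **Allergic reaction to the ICS.** This is a separate named risk with its own rule in VII.C.2 and VII.C.5: the patient and care site are notified and participation ends. It is not one of the seven.

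3. **Contact with patients.** II.C.7 requires no study visit after enrolment. II.B describes the monthly questionnaire as covering exacerbations, symptoms, medication use and visits driven mainly by asthma. The full-study schedule in II.D.2(b) lists no adverse-event domain; its only item on another illness after baseline is the COVID-19 questionnaire. The item wording is not in the documents, so this step rests on the description and the schedule.

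4. **Records.** III.D.4 draws on claims where a site has access, and on billing and EHR data for integrated systems. II.E.1 asks all sites for their own billing data. III.E.7 summarises "total number of ED visits, and total number of hospitalizations" for any cause, separately from the asthma-related counts, and compares the arms. Non-asthma admissions would therefore appear in these data where access allows. They are exploratory counts, and nothing connects them to the PI or to the notice period in VII.C.6.

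5. **Promised reports against sources.**
   - *SAE notice to the PI and IRB (VII.C.4(c), VII.C.6):* covers any cause. No detection route is stated for non-asthma events. This is a direct conflict with VII.C.4(b).
   - *Adverse event rates for the safety officer (III.E.9):* the scope is not stated. Asthma events alone could satisfy the wording.
   - *Adverse events as possible covariates in the censoring model (III.E.10):* an illustrative list, which asthma events could also satisfy.

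The firm contradiction is between VII.C.4(b) and VII.C.4(c)/VII.C.6. Sections III.E.9 and III.E.10 are ambiguous, not contradictory.

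**The case against.** The best defence is that light safety monitoring is a declared pragmatic choice, in patients who are all already prescribed daily ICS, with the study drug a familiar one. Possible overuse is watched: the pharmacy alerts central staff when a patient asks for a third refill in a month (VII.B.1). Reasons for dropout are recorded (III.E.10). This explains why minor events are not collected. It does not explain a promise of all-cause SAE reporting without a described source.

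A reader might infer more than the documents support:

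- *That no study-drug risk is handled.* Allergic reaction to the ICS has its own rule.
- *That non-asthma serious events leave no trace.* All-cause ED visits and hospitalizations are gathered and compared by arm where site data permit.
- *That the PI cannot learn of non-asthma SAEs, or that the safety officer's rates consist of asthma events only.* The route in VII.C.6 is unspecified, not excluded. VII.C.4(b) itself allows a non-asthma illness to end participation, which presupposes that some such events become known.

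These limits stand, and the point is confined accordingly.

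Timing also counts. Figure 3 ends patient follow-up on 1 May 2021. Section X cites a May 2021 publication and plans to contact patients who have left the study. New monthly survey items may therefore come too late.

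**Conclusion.** The concern holds in this form: VII.C.4(b) conflicts with VII.C.4(c) and VII.C.6, no described procedure brings a non-asthma SAE to the PI, and none of the seven listed ICS side effects has a described collection route. It affects both arms, in up to 1210 patients over 12 to 15 months. The number of events missed cannot be estimated, because the documents give no background rates and do not say how many sites can supply complete records.

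The primary efficacy analysis is not affected. What is affected is compliance with the trial's own SAE commitment and any statement about the tolerability of the strategy. The conclusion assumes that the monthly survey matches its description and that no separate safety manual, absent from these documents, sets out SAE detection.

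**What to change.** **Reconcile the text.** Replace the opening sentence of VII.C.4(b) so that it agrees with VII.C.4(c) and VII.C.6, and say who detects a non-asthma SAE and how it is passed on. State in III.E.9 which adverse events the safety officer's rates include.

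**If surveys are still running,** add to the monthly survey, in both arms, one item on any overnight hospital stay for any reason and a short tick-list of the three common ICS effects. Forward hospital stays and known deaths to the PI as SAEs, with the VII.C.6 period starting when the study becomes aware.

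**In any case,** tabulate all-cause hospitalizations and ED visits by diagnosis and arm from the records already requested, with the number of patients whose records are available. Include diagnoses matching the four less common effects. The planned asthma-related counts already depend on diagnosis, so the field is needed anyway. State in the report that non-asthma harms were otherwise not systematically collected, so the trial cannot draw a conclusion on ICS side effects.

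**Cost.** A protocol amendment and one table from data already requested. If surveys continue, add a slightly longer questionnaire and more SAE paperwork. Two weaknesses remain: self-report in an open-label trial, which the records table offsets only in part, and incomplete records at some sites.

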#### **(c) Serious Adverse Events:**

These are events that meet any of the following criteria: results in death, is life- threatening, requires or prolongs hospitalization, results in persistent/significant disability, or results in a congenital anomaly/birth defect. Also includes any other adverse event that, based upon appropriate medical judgment, may jeopardize the subject's health and may require medical or surgical intervention to prevent one of the outcomes listed above.

### **5. Management of Asthma Exacerbations**

This study is directed toward the reduction of asthma exacerbations. Acute management of subjects' asthma is not changed or mandated by the study and will be handled by the patient's chosen clinician in their usual manner. Training clinicians with the Asthma IQ instructional component as support for standardized provider educated care has been shown to improve asthma control and may be associated with decreased risk of exacerbations. The use of PARTICS (combined ICS+SABA) for acute symptom relief is intended to further reduce the risk of exacerbations and no data have been published to show that the use of combined acute relief medications increases exacerbation potential.

Data collection will include assessment of exacerbations, with confirmation through communication with the patient's primary site of asthma care. Due to the pragmatic nature of the study, no additional interventions will be provided unless the patient has an allergic reaction to the components of the ICS used for this study. If such is the case both the patient and their care site will be notified to assure they have information on the exact medication to which the

apparent allergic reaction occurred and the patient's participation in the study will be discontinued since no other options for a different type of ICS are available within the study.

## **6. Data and Safety Monitoring Plan**

We will appoint an independent safety officer from the Division of Pulmonary and Critical Care Medicine from Brigham and Women's Hospital who has no other role in the PREPARE trial. This independent safety officer will be presented data in a blinded manner, and review safety data twice annually.

The PI of the study will be informed of serious adverse events as soon as they occur and will notify the central IRB at Partners within 5 working days/7 calendar days.

## **7. Risk to Data Confidentiality**

Potential risks to data confidentiality will be mitigated by requirements for the de-identification of study data before secure transfer from the University of Colorado data collection site to Duke and by security protocols for the IHC patient-reported outcomes data capture systems. All users of the IHC system will be tracked and only provided access in a secure fashion following established UC-DFM Standard Operating Procedures for this process. The IHC system is an enterprise level system that handles multiple research and clinical data collection processes across thousands of individuals simultaneously. This project will be totally isolated from all other ongoing research activities. Patients will only have access to their personal information, questionnaires appropriate for their current research activities and the educational video(s) associated with their arm of the study. Site research staff will only have access to the patients enrolled by their site. AAFP NRN staff will have access to patient contact data for all patients, as well as reports indicating questionnaire status for each individual. The IHC system will automatically lock the monthly questionnaire for three weeks following completion by an individual assuring that we do not have duplicate completion of one month's questionnaire. The system will automatically remind individuals to complete questionnaires and unlock them at appropriate times. Missed questionnaires will not be locked until another questionnaire is completed. The risks of loss of confidentiality are minimal given the secure, central handling of these data.

## **8. Inclusion of Women and Minorities**

Only African American and Hispanic/Latino adults ages 18 years and older with asthma will be enrolled in this study, as the proposed research question focuses on the treatment of asthma specifically in this population. Based on past research experience and evidence from the medical literature, the researchers feel that this population is at significantly higher risk from asthma than other racial and ethnic groups and that further study in this specific population is needed. Therefore, no other racial/ethnic groups will be enrolled.

Women will be enrolled with no exclusion for pregnancy if determined acceptable by the woman's maternity care clinician(s). Statistics for studies of this type indicate that the percentage of women within the population to be enrolled will be approximately 60%. The study will seek to enroll approximately 50% of subjects of African American self- reported race and approximately 50% of Hispanic/Latino self-reported ethnicity with the provision as stated above that those reporting themselves to be Black and Hispanic will be enrolled in the H/L group. Enrollment of one group may be slowed or stopped if recruitment is faster or recruitment goals

are met for this group. The expected enrollment is detailed in the section XII, Table 1.

## **9. Inclusion of Children/Adolescents**

Patients ages 18 to 21 will be included in this study. While they are labeled as “children” for study inclusion criteria by the National Institutes of Health and the Department of Health and Human Services, no special requirements for informed consent or parental permissions or safety concerns exist for this study among those aged 18 to 21 at all sites, except for the University of Puerto Rico—UPR requires assent of children ages 18 to 21 plus consent of a legal guardian.

## **D. Potential Benefits and Importance of the Knowledge to be Gained**

### **1. Benefits to Human Subjects and Others**

We believe there may be a potential benefit to those patients randomized to the PARTICS arm but this is still unknown. The potential benefit would be decreased numbers of exacerbations (asthma episodes that require oral steroid bursts or hospitalizations) and possibly decreased symptoms and reduced need for extra asthma medications. It is also possible that implementation of the Asthma IQ training for standardized provider educated care may improve rates of asthma control and this benefit could accrue to patients *in both arms* of the study.

Asthma has been resistant to various approaches to improve outcomes. Most approaches to date have focused in improving clinician implementation of current clinical guidelines and improving patient adherence with these treatment guidelines but when successful have been complex and difficult to widely disseminate. A few projects have worked at the community level to improve environmental conditions, but are also difficult to disseminate widely.

The approach studied in this project puts the patient in control of the level of additional use of ICS controller medications. The potential for benefit to society and individuals with asthma in general is very significant as the PARTICS represents a new approach to asthma therapy. Current asthma controller therapy follows a rigid, provider- prescribed approach. This study will examine the potential benefits of a patient controlled approach added to typical use of daily controller medications. Multiple studies and quality improvement projects have attempted to reduce asthma exacerbations, a theoretically ambulatory care-sensitive condition, with little long term improvement in outcomes. Any chance to determine a method to close this gap in care and learn how better to treat these subjects in clinical practice presents a clear benefit to African American and Hispanic/Latino adults with asthma.

Our proposed study seeks to inform a key health decision for people with asthma and clinicians who treat it-- should asthma patients use, and providers prescribe, a controller medication to be used each time a reliever is used in order to reduce asthma exacerbations? The PREPARE trial can help with that decision by assessing the ability of PARTICS to reduce exacerbation occurrences, reduce days lost from school or work, and reduce the consumption of ICS – all outcomes of high importance to patients.

This health decision is particularly pertinent among AAs and H/Ls, who bear a disproportionate burden of asthma morbidity and are less likely to receive, choose, or be able to comply with guideline-driven care. If the study shows that the PARTICS approach reduces exacerbations and/or improves other outcomes important to patients, then this approach can easily be adopted by patients and their providers in the context of current care since it is intuitive and

takes advantage of current patient-driven patterns of reliever inhaler use.

